5. INVESTIGATIONAL PRODUCTS

5.1. VRx-3996 Drug Substance

VRx-3996 is a hydroxamic acid-based HDAC inhibitor.¹⁸ As is typical of this class, the structure of VRx-3996 has 3 main components: a hydroxamic acid that coordinates with the Zn^{2+} ion in the active pocket of the enzyme, a spacer (azabicyclo pyrimidine) that fills out the narrow channel of the binding site, and a hydrophobic head group, amino methyl(fluoroquinoline), that interacts with the rim surrounding the pocket of the active site.

Figure 1: Structural Formula and Key Features of VRx-3996

Specific characteristics of VRx-3996 are outlined in [Table 9](#).

Table 9: Drug Substance Properties

Molecular formula	C ₂₀ H ₁₉ FN ₆ O ₂
Molecular weight	394.40
Physical description	Off-white to pale orange solid
LogP	1.60 (neutral); -1.0 (cationic)

5.1.1. Acquisition

VRx-3996 will be provided by the Sponsor to each clinical site. Instructions for requesting and receiving VRx-3996 will be included in the Study Manual.

5.1.2. Dosage Form

VRx-3996 drug product is currently supplied as 5 mg strength capsules. In addition to active ingredient nanatinostat, inactive excipients consist of silicified microcrystalline cellulose and sodium stearyl fumarate, which are dry-filled into size 2, white to off-white, opaque, hard gelatin capsules for oral administration.

Viracta intends to introduce film-coated immediate-release (IR) tablets of 5 mg and 10 mg strengths in this study, replacing the capsule product. The tablets are dose proportional, consisting of the active VRx-3996, and inactive excipients (i.e., mannitol, microcrystalline cellulose, croscarmellose sodium, and sodium stearyl fumarate). The tablets are film coated with non-functional Opadry II white. The comparability between the tablets and capsules has been established via *in vitro* dissolution studies and *in vivo* dog pharmacokinetic studies and no dose adjustment is needed.

All of the inactive ingredients in the drug product meet compendial requirements of the United States Pharmacopeia and/or National Formulary.

5.1.3. Composition

The quantitative compositions for 5 mg VRx-3996 capsules are presented in [Table 10](#).

Table 10: Quantitative Composition of VRx-3996 Capsules

Components	5 mg	
	Amount per Capsule (mg)	Weight (%)
VRx-3996	5.0 ¹	2.5
Silicified microcrystalline cellulose	194.0	97.0
Sodium stearyl fumarate	1.0	0.50
Total (Blend)	200.0	100.00
Capsule Size	61.0 ²	---
Total (filled capsule)	261.0	---

¹ Exact amount is corrected for drug substance assay (free base on the anhydrous, solvent free basis)

² Average capsule weights as provided by manufacturer

The quantitative compositions for the dose proportional 5 mg and 10 mg VRx-3996 tablets are presented in [Table 11](#).

Table 11: Quantitative Composition of Film-Coated, Immediate-Release VRx-3996 Tablets (5 and 10 mg Strengths)

Component	Function	% w/w	5 mg strength (mg/tablet)	10 mg strength (mg/tablet)
VRx-3996	Drug substance	5.0	5	10
Mannitol	Filler	25.0	25	50
Microcrystalline cellulose	Filler	65.5	65.5	131
Croscarmellose sodium	Disintegrant	4.0	4.0	8.0
Sodium stearyl fumarate	Lubricant	0.5	0.5	1.0
Total (core)		100	100	200
Opadry II coating powder	Film coating	3.0	3.0	6.0
Purified water*	Film coating	-	-	-
Total			103	206

* Used to make the coating solution and removed during processing

5.1.4. Product Packaging

VRx-3996 Capsules, 5 mg, are packaged in 30-count high-density polyethylene bottles, sealed and closed with child-resistant caps.

VRx-3996 film-coated Tablets, 10 mg and 5 mg, are packaged in 45-count high-density polyethylene bottles, sealed and closed with child-resistant caps.

5.1.5. Product Storage and Stability

VRx-3996 should be stored at controlled room temperature 20–25°C (68–77°F), with excursions permitted to 15–30°C (59–86°F) in a secure location. Once the bottle seal is broken, bottles should be stored tightly capped.

5.1.6. Dosing and Administration

VRx-3996 will be administered in the Phase 1b portion of the study at a dose and schedule determined by the assigned cohort.

In the Phase 2 portion of the study, patients will receive VRx-3996 at the RP2D and schedule determined in the Phase 1b portion of the study.

5.1.7. Dietary Requirements

There are no special dietary restrictions or requirements associated with VRx-3996; however, valganciclovir absorption is affected by food and should be taken with food (see [Section 5.2.4](#) for additional clarification).

5.1.8. Dose Adjustments/Modifications/Delays

Given the expectation that both study drugs are required for activity, both agents will be held and restarted in parallel unless toxicity is clearly associated with VRx-3996 and there is clinical justification to continue dosing with valganciclovir alone. For non-hematologic toxicity requiring dose modification see [Table 12](#).

Table 12: Requirements for Dose Hold Secondary to Non-Hematologic Toxicity

Toxicity (CTCAE)	Requirement for Dose Hold
Grade 1 or 2	No dose hold required
Grade 3+	Hold subsequent dosing until toxicity has resolved to at least Grade 1 or baseline

In the event that any of the following hematologic AEs are observed on study, the dose of VRx-3996 and valganciclovir will be held:

- ANC <500 cells/ μ L
- PLT count <35,000/ μ L
- Hemoglobin (HGB) is <8 g/dL

If a hold is implemented for study drug-related toxicity, patients may restart study drugs only if the following conditions are met or if agreed with the Medical Monitor:

- The AE has resolved to at least Grade 1 or baseline for non-hematologic AEs and Grade ≤ 2 hematologic toxicity related to study drug
- The AE is not expected to recur in the opinion of the Investigator with subsequent study drug administration based on an intervention such as prophylactic use of appropriate treatment (e.g., prophylactic anti-emetics), or a reduction in the dose of one or both of the study drugs
- Continued administration of study drugs is considered to be in the patient's best interest based on the opinion of the study Investigator

Patients should be followed up approximately twice weekly for resolution of the toxicity. Study days will continue to accrue during dose holds and other scheduled procedures as per [Table 15](#) should not be delayed. If the dose is held for more than 14 days, the Investigator should consult with the Medical Monitor before dosing resumes.

If a patient has multiple dose interruptions for study drug toxicity or has had to interrupt for more than 14 days, a dose reduction should be considered. Dose reduction for VRx-3996 will be in 10 mg increments and for valganciclovir from 900 mg to 450 mg. Re-escalation of study drug dose may only be performed after approval by Medical Monitor.

There are additional criteria for modification of the valganciclovir dose based on renal function as outlined in [Section 5.2.3](#).

5.2. Valganciclovir

5.2.1. Acquisition

Valganciclovir tablets will be provided to the clinical sites from commercial sources by the Sponsor. Instructions for requesting and receiving valganciclovir will be included in the Pharmacy Manual.

5.2.2. Product Storage and Stability

Valganciclovir should be stored at controlled room temperature 20–25°C (68–77°F), with excursions permitted to 15–30°C (59–86°F) in a secure location.

5.2.3. Dosing and Administration

In the Phase 1b portion of the study, the starting dose of valganciclovir is listed in [Table 5](#). If a patient is on valganciclovir prior to study entry, the dose of valganciclovir should be increased to the dose and schedule listed for their assigned cohort in [Table 5](#). Patients who have previously shown intolerance to a given dose of valganciclovir, should start at their highest tolerable dose of valganciclovir or their assigned dose (whichever is lower) following discussion with the Medical Monitor. For those patients with evidence of renal impairment at study entry, the starting dose of valganciclovir should be discussed with the Medical Monitor but should be no higher than the doses listed in [Table 13](#).

In the Phase 2 portion of the study, the starting dose and schedule of valganciclovir (i.e., RP2D) will be determined by the SRC at the conclusion of the Phase 1b portion of the study. If a patient is on valganciclovir prior to study entry, the dose of valganciclovir should be increased to the RP2D. Patients who have previously shown intolerance to a given dose of valganciclovir, should start at their highest tolerable dose of valganciclovir or the RP2D (whichever is lower) following discussion with the Medical Monitor. For those patients with evidence of renal impairment at study entry, the starting dose of valganciclovir should be discussed with the Medical Monitor but should be no higher than the dose listed in [Table 13](#).

In either phase of the study, patients who develop an elevated creatinine while on study should have their dose of valganciclovir reduced to no higher than the doses listed in [Table 13](#). For patients already receiving a dose of valganciclovir lower than that recommended in [Table 13](#), the Investigator should discuss the amount of dose reduction with the Medical Monitor.

Table 13: Valganciclovir Dose Adjustments for Adult Renal Impairment

Creatinine clearance (mL/min)	Valganciclovir dose
≥60	900 mg once daily
40–59	450 mg once daily
25–39	450 mg every 2 days
10–24	450 mg twice weekly
<10 (on hemodialysis)	Not recommended (discuss with Medical Monitor)

In patients who are unable to tolerate oral dosing of valganciclovir, the Investigator will have the option of administering ganciclovir IV at 5 mg/kg IV BID. In patients who are receiving a dose of valganciclovir less than 900 mg PO BID, the dose of ganciclovir will be reduced accordingly using the ratio of 900 mg valganciclovir to 5 mg/kg ganciclovir.

The SRC may elect to adjust the starting dose or schedule of valganciclovir as appropriate during the conduct of the study.

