1.9. Valganciclovir

Valganciclovir (VALCYTE[®]), an oral prodrug of ganciclovir, is approved for treatment of CMV retinitis in patients with AIDS and prevention of CMV disease in high-risk transplant patients. Outside of its approved indications, valganciclovir has been shown to be effective in mitigating EBV viral load in EBV⁺ pediatric liver transplant patients at risk for development of post-transplant proliferative disorder.²⁰ Recommended adult dosing for treatment of CMV retinitis is 900 mg orally twice daily (BID) for 21 days followed by a maintenance dose of 900 mg once a day.

Oral valganciclovir is well absorbed (~60%) and converted to ganciclovir by first-pass intestinal or hepatic metabolism with peak plasma concentrations achieved in 1 to 3 hours. The major elimination pathway is renal excretion of ganciclovir through glomerular filtration and active tubular secretion. Dosage reductions, based on creatinine clearance, are recommended for patients with renal impairment. The antiviral activity of valganciclovir is based on the generation of ganciclovir-triphosphate, which is a competitive substrate for the CMV DNA polymerase. Significant AEs include hematologic toxicity and acute renal failure. Hematologic toxicity may result in leukopenia, neutropenia, anemia, and thrombocytopenia. The VALCYTE[®] package insert includes guidance regarding pre-treatment hematologic assessment and complete blood count (CBC) monitoring. Elderly patients, patients receiving nephrotoxic drugs and inadequately hydrated patients are at higher risk for renal failure. Other common AEs include gastrointestinal manifestations, such as diarrhea, nausea, and vomiting.

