4. STUDY ELIGIBILITY

4.1. Inclusion Criteria

1. Signed, informed consent
2. Age 18 or more years
3. ECOG PS²⁶ of 0 to 2 or Karnofsky Performance scale (KPS) $\geq 60\%$
4. Failed any available standard therapy with a reasonable likelihood of clinical benefit (e.g., anti-CD20 monoclonal antibody, withdrawal of immunosuppression, cytotoxic chemotherapy)
5. Relapsed/refractory, pathologically confirmed EBV⁺ lymphoid malignancy or lymphoproliferative disease regardless of histologic subtype
6. EBV⁺ as determined by institution's usual testing method or by the Sponsor's central laboratory on a specimen that is representative of the current disease (e.g., for patients who have relapsed the biopsy specimen should have been taken post-relapse). For questions on the suitability of particular specimens, please consult the Medical Monitor
7. Absence of available therapy with reasonable likelihood of cure or significant clinical benefit
8. Evaluable [Phase 1b only] or measurable [Phase 1b and Phase 2] disease based on Recommendations for Initial Evaluation, Staging, and Response Assessment of Hodgkin and Non-Hodgkin Lymphoma: The Lugano Classification²²
9. If previously treated:
 - a. Treatment-related toxicity resolved to at least Grade 1 (alopecia excepted), or
 - b. Treatment-related toxicity resolved to at least Grade 2 with prior approval of the Medical Monitor, or
 - c. Treatment related toxicity resolved to at least the levels outlined in inclusion criterion #10, without transfusion support.
10. Adequate laboratory parameters including:
 - a. Absolute neutrophil count (ANC) $\geq 1000/\text{mm}^3$
 - b. Platelet (PLT) count $\geq 50,000/\text{mm}^3$
 - c. Hemoglobin $\geq 8.0 \text{ g/dL}$
 - d. Asparagine aminotransferase (AST)/serum glutamine oxaloacetic transaminase (SGOT), alanine aminotransferase (ALT)/serum glutamic-pyruvic transaminase (SGPT) $\leq 3.0 \times$ upper limit of normal (ULN) ($\leq 5 \times$ ULN if known liver involvement)
 - e. Total bilirubin $\leq 2.0 \times$ ULN unless considered due to Gilbert's syndrome in which case, $\leq 3.5 \times$ ULN

- f. Estimated glomerular filtration rate (eGFR) ≥ 60 mL/min/1.732 m² by Modification of Diet in Renal Disease (MDRD) equation
- g. Prothrombin time (PT) $\leq 1.5 \times$ ULN
- h. International normalized ratio (INR) $\leq 1.5 \times$ ULN
- i. Serum potassium and magnesium should be within normal limits for institution or treatment to correct out of range values should be instituted

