5.2.5. Dose Adjustments/Modifications/Delays

Dose adjustments for valganciclovir will be made in concert with adjustments to VRx-3996. See [Section 5.1.8](#) for specific details.

For patients with renal impairment, dose adjustments for valganciclovir will be made in accordance with valganciclovir prescribing guidelines as outlined in [Table 13](#).

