Informed consent – Informed consent may be performed at any time prior to the start of screening procedures.

EBER/histology Sample – Histology sample, indicative of current disease, to be sent to central pathology lab at the time of screening. Central pathology review/results not required for enrollment. Pathology review will include detection of EBV gene products.

Medical history – Record all cancer-related history over the patient's lifetime and collect non-cancer related history for the 2 years prior to study entry. For transplant recipients (except auto-SCT), collect the following historical information on donors: HIV1, HIV2, hepatitis B surface Ag, hepatitis B surface Ab, hepatitis B core Ab, hepatitis C Ab, HSV-1 Ab, HSV-2 Ab, CMV Ab IgG, CMV Ab IgM, EBV IgG-VCA (viral capsid antigen).

Vital signs – Performed just prior to first dose of valganciclovir and VRx-3996, and in concert with (but prior to) PK draws on Cycle 1 Day 1. On other indicated visit days, perform vital signs once (prior to study drugs dosing if administered in clinic). Vital signs include weight (in pounds), heart rate, respiratory rate, blood pressure, temperature, and oxygen saturation by pulse oximeter. Note that weight only needs to be recorded once daily.

Performance status – Either ECOG or KPS (See [Table 16](#) in the Appendix for conversion table).

Concomitant medications – Recorded from 28 days prior to Cycle 1 Day 1 to 28 days after last dose of study drugs, except for concomitant medications related to cancer treatment, for which lifetime history prior to entering the study will be recorded.

Urinalysis – [Urine] Color, appearance, glucose, bilirubin, ketone, specific gravity, blood, pH, protein, urobilinogen, nitrite, leukocyte esterase, RBC, WBC, epithelial cells.

Hematology - [Blood] Complete blood count with differential to include WBC, RBC, HGB, HCT, platelets, MCV, MCH and differential.

Chemistry - [Blood] Sodium, potassium, chloride, bicarbonate, blood urea nitrogen, creatinine, glucose, calcium, phosphate, magnesium, AST, ALT, total bilirubin, alkaline phosphatase, total protein, albumin, uric acid, and LDH.

Coagulation – [Blood] PT, PTT, and INR.

Serum pregnancy test – Only required for females of child-bearing potential.

Urine pregnancy test – Only required for females of child-bearing potential at the beginning of every cycle.

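### Table 13 limits valganciclovir by creatinine clearance, but nothing at entry requires a clearance, so some older, lighter patients with unremarkable creatinine could start above its limit

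*Protocol*

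**What the plan says.** **Dose limit.** Table 13 (Protocol 5.2.3) allows 900 mg once daily at a creatinine clearance of 60 mL/min or more, 450 mg once daily at 40–59, and less below that. It names no formula. Protocol 1.9 gives the same basis: "Dosage reductions, based on creatinine clearance, are recommended for patients with renal impairment".

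**Who is sent to Table 13.** There are three routes:
- At entry (5.2.3): "For those patients with evidence of renal impairment at study entry, the starting dose of valganciclovir should be discussed with the Medical Monitor", with the table as the ceiling.
- On study (5.2.3): "patients who develop an elevated creatinine while on study should have their dose of valganciclovir reduced" to the table's limits.
- In general (5.2.5): "For patients with renal impairment, dose adjustments for valganciclovir will be made in accordance with valganciclovir prescribing guidelines", as set out in Table 13.

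Neither renal impairment nor elevated creatinine is defined.

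**What is measured.** Criterion 10f requires an eGFR of at least 60, indexed to body surface area, "by Modification of Diet in Renal Disease (MDRD) equation". The chemistry panel includes "bicarbonate, blood urea nitrogen, creatinine, glucose, calcium, phosphate, magnesium", and the vital signs note reads "Vital signs include weight (in pounds), heart rate, respiratory rate". The Schedule of Events lists no creatinine clearance. The only clearance formula in either document is Cockcroft-Gault in SAP 4.5.4, where it serves laboratory summaries and plots.

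**Dose and population.** Protocol 3.2.4 and 3.3 give valganciclovir 900 mg once daily in Phase 2 and the tablet cohort. The age criterion is "Age 18 or more years", with no upper limit.

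**The concern.** Eligibility and dosing use different measures of renal function. MDRD eGFR has no weight term and is indexed to body surface area. Table 13 needs an absolute clearance, which by Cockcroft-Gault falls with lower weight and, more steeply than MDRD, with age. An older, light patient can pass 10f comfortably and still belong in the 40–59 band.

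The entry route depends on evidence of renal impairment, but the one required renal test flags no eligible patient. The on-study route needs a creatinine that becomes elevated, so a stable entry value does not trigger it.

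At stake is the starting dose of a renally eliminated drug. Protocol 1.12.1 says its renal and platelet toxicity overlaps with that of VRx-3996, and Protocol 1.9 names elderly patients as at higher risk of renal failure.

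**Working it through.** The plan states no figure to reproduce here. The check asks whether one patient can meet 10f and yet fall below 60 mL/min for Table 13.

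**Inputs**
- Clearance (SAP 4.5.4): CG = (140 − age) × kg / (72 × Cr), × 0.85 for women, with Cr in mg/dL. Applying it to Table 13 is an assumption.
- MDRD: the documents do not print the equation. Assumed: k × Cr^−1.154 × age^−0.203, × 0.742 for women, no race term, with k = 175 or 186 as a range.
- Exposure: assumed inversely proportional to clearance. The reference is 900 mg once daily at CG 60, so the ratio at the same dose is 60/CG.

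**Worked case: man, 75 years, 60 kg, creatinine 1.0 mg/dL**
- MDRD = 175 × 75^−0.203 = 72.8 (77.4 with k = 186). He meets 10f.
- CG = 65 × 60 / 72 = 54.2. Table 13 allows 450 mg once daily.
- Exposure at 900 mg once daily: 60 / 54.2 = 1.11 times the reference.

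**Creatinine window in which 10f is met but CG is below 60**

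Lower end (CG = 60): Cr = (140 − age) × kg × (0.85 if female) / 4320. Upper end (MDRD = 60): Cr = (k × age^−0.203 × (0.742 if female) / 60)^(1/1.154). Paired values are for k = 175 / 186.

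| Patient | Lower Cr | Upper Cr | CG at upper end | 60/CG |
|---|---|---|---|---|
| Man 75, 60 kg | 0.90 | 1.18 / 1.25 | 45.8 / 43.4 | 1.31 / 1.38 |
| Woman 75, 60 kg | 0.77 | 0.91 / 0.96 | 50.4 / 47.8 | 1.19 / 1.26 |
| Man 65, 60 kg | 1.04 | 1.21 / 1.28 | 51.5 / 48.9 | 1.17 / 1.23 |
| Woman 65, 60 kg | 0.89 | 0.94 / 0.99 | 56.7 / 53.8 | 1.06 / 1.12 |
| Man 75, 70 kg | 1.05 | 1.18 / 1.25 | 53.4 / 50.7 | 1.12 / 1.18 |
| Woman 75, 70 kg | 0.90 | 0.91 / 0.96 | 58.8 / 55.8 | 1.02 / 1.08 |
| Man 65, 70 kg | 1.22 | 1.21 / 1.28 | 60.1 / 57.0 | none / 1.05 |
| Woman 65, 70 kg | – | 0.94 / 0.99 | 66.2 / 62.8 | none |

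**Where the mismatch stops, and where it grows**
- At 80 kg and ages 65 or 75 there is no window, except for the 75-year-old man with k = 186 (CG 57.9 at the limit).
- Low weight alone is not enough: a woman of 45 years and 60 kg has CG 67.3 (63.9) at the 10f limit.
- A man of 70 years and 70 kg with creatinine 1.0 has MDRD 73.9 and CG 68.1, so the two measures agree.
- Lighter patients are affected at lower creatinine: a woman of 75 years and 50 kg with creatinine 0.8 has MDRD 69.9 (74.3) and CG 48.0.

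**The case against.** **Table 13 cannot be read without a clearance.** This is correct. A reader might infer that the protocol never calls for one. The documents do not support that, because once any route sends a patient to the table, someone must obtain a clearance to find the row. The gap is earlier: nothing requires a clearance to decide who is sent.

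**The text already points to clearance.** Criterion 10f excludes eGFR below 60, so the entry sentence has little purpose unless it looks beyond 10f. Protocol 1.9 bases reductions on clearance, the Medical Monitor approves every registration (6.2), and the Study and Pharmacy Manuals, which are not available here, may cover the step. Any of these could catch the patient, but the protocol itself does not require it.

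**The breach depends on the formula.** This stands as a limit on the claim. If a site converted the eGFR to mL/min by body surface area, the worked case would be 72.8 × BSA / 1.73. With the Mosteller formula (an assumption) and heights of 150–180 cm, BSA at 60 kg is 1.58–1.73 m². The result is about 67–73 mL/min, and 900 mg once daily is then within Table 13. It would be too strong to say that these patients definitely exceed the limit, since the protocol names no formula. That silence is itself part of the gap.

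**The harm is small and monitored.** Chemistry and hematology are drawn on Cycle 1 Days 1, 2, 8, 15 and 22, and the hold rules in 5.1.8 apply. The largest ratios also occur at the highest creatinine values, where an investigator is most likely to look twice. This supports a minor rating. It does not remove the point, because these safeguards act mainly after dosing has begun.

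**Conclusion.** The point holds as a gap in identifying patients for the starting dose. No clearance is required at entry, the entry trigger is undefined, and the one required renal test is passed by everyone eligible. Some older, lighter patients with unremarkable creatinine could therefore follow the protocol and start at 900 mg once daily where Table 13 allows 450 mg.

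This rests on reading Table 13 as Cockcroft-Gault and on assumed MDRD coefficients. The excess exposure is modest on the further assumption of inverse proportionality to clearance. How often it would occur cannot be estimated, because the documents give no age or weight distribution.

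A reader might infer that the dosing rule is absent or that the efficacy analysis is compromised. Neither follows: the rule exists, and ORR, sample size and error rates are not affected. Rating: minor; a cheap improvement for patient safety.

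**What to change.** Add to Protocol 5.2.3: *Calculate Cockcroft-Gault creatinine clearance (SAP 4.5.4 formula, weight in kg) at screening; a value below 60 mL/min is evidence of renal impairment, and the starting valganciclovir dose must be no higher than Table 13.* State in Table 13 that its bands use this formula, and include the screening value in the registration materials.

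Keep the on-study trigger of elevated creatinine and recalculate clearance when it fires. Clearance alone would miss some patients: a man of 50 years and 90 kg whose creatinine rises to 1.6 mg/dL has CG = 90 × 90 / (72 × 1.6) = 70.3, yet the current text reduces him from Cohort 1's 900 mg twice daily to 900 mg once daily. Recalculating at every chemistry panel is not advised. It goes beyond the starting-dose gap, and values near 60 could move a patient back and forth between doses. Re-escalation stays subject to Medical Monitor approval (5.1.8).

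**Cost.** One sentence, a table note and one registration field. Age, weight (recorded in pounds, so it needs conversion) and creatinine are already collected, so no new test or visit is needed. The downside is that a few patients start at 450 mg once daily instead of 900 mg. Under the same exposure assumption, the worked-case patient would then have 0.5 × 60 / 54.2 = 0.55 times the reference exposure, and a patient at CG 43.4 would have 0.69. This matters because 5.1.8 expects both drugs to be needed for activity, but the step is Table 13's own.
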